2.1 Trial design

The study is designed as a single-centre, placebo-controlled, double-blind and randomized controlled trial with a balanced 2x2 crossover design and a washout period between treatment arms. Specifically, half of the recruited patients will be treated with spermidine for eight weeks, followed by placebo for eight weeks. The other half of patients will first receive placebo and then spermidine. There will be a washout period of four weeks between the first period of eight weeks and second period of eight weeks to separate the two interventions in both arms, which will avert any carryover or residual effects. A balanced 2x2 crossover trial design is ideal for this study for the following two reasons:

(i) Physiological reason: spermidine levels in the body are substantially affected by the diet. Thus, patients with different dietary habits could already have different spermidine levels at baseline (i.e. before starting the trial). Even if patients were randomized into 2 groups correcting for baseline measured circulating spermidine, this wouldn't guarantee that spermidine levels in the body tissues are comparable without confirming via biopsy, not to mention that food intake would need to be strictly controlled and be identical in both arms throughout the trial. For this reason, crossover/repeated measurements are not only more practical, but rather essential for our proposed study. The effect of any other confounding factors (e.g. body mass index, age, smoking, baseline blood pressure, LDL, etc.) will be also reduced to a minimum as every patient will serve as his/her own control.

(ii) Statistical reason: a crossover design is particularly efficient as it provides the highest power-to-sample size ratio. Thus, the study endpoints can be examined with as few patients as possible.

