2.6 Sample size considerations

As outlined in 2 and 2.1., the blood pressure-lowering effect of spermidine is well established in animal models. Furthermore, 28 elderly patients with subjective declining cognitive function within the SMARTAGE trial revealed a drop in systolic blood pressure of 10 mmHg (4.5 mmHg more than in the placebo group) upon spermidine (1.2 mg/day) supplementation for three months. In the proposed trial, we will use a three-fold higher dose of spermidine and we will enroll patients with a higher baseline blood pressure (≥ 150 and ≤ 180 mmHg systolic BP). Therefore, we expect a reduction of systolic blood pressure of at least 5 mmHg. To this end, we calculated that a total of 38 patients would be sufficient to detect that effect at a power of 80%, assuming a two-tailed α value (type-I error) of 5%, blood pressure variance (SD) of 13 mmHg and within-subject correlation coefficient (r) of 0.65. We expect a drop-out rate of 15% due to the 20-week-long duration of the trial, thus, a total number of 46 patients will be enrolled.

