2.8 Project duration and milestones

We envision that a period of 21 months will be needed to successfully accomplish this study. The recruitment (18 months) is planned as follows:

First patient visit:	February 2020
Last patient enrolled:	June 2021

3 Methods

3.1 24h BPM

During each of the four visits patients will be supplied with an ambulatory blood pressure measurement (ABPM) device (Mobil-O-Graph® PWA, I.E.M. GmbH, Stolberg, Germany). After 24 hours of continuous BPM at their homes, patients will remove the device and return it to the study center via postal service. Mobil-O-Graph® PWA is a well established device to measure central blood pressure and pulse wave velocity used and validated in multiple clinical trials and settings. Despite being a non-invasive technique good accuracy compared to intra-aortic readings has been proven (linear correlation $R=0.81$, $p < 0.0001$) in 120 patients (see validation data on www.iem.de/en/health-management/studies-validations.html and a bibliography at www.iem.de/files/content/DE/IEMintern/Support/Hintergründe/Bibliography%20Mobil-O-Graph%20Blood%20Pressure%20PWA%202.9.pdf) During the visit on-site blood pressure measurements and a standardized 6MWT will be conducted at every visit.

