The effect of distinct treatments (spermidine or placebo) on a given parameter (e.g. SBP) will be expressed as a change score from baseline (Δ). The difference between treatment effects will then be evaluated using a mixed linear model, where *Subjects* will be included as a random factor, whereas Treatment (spermidine vs. placebo), *Period* (first vs. second), and *Sequence* (spermidine-placebo vs. placebo-spermidine) will be fixed factors (i.e. predictors). Although we expect no carryover effects due to the washout period, including *Period* and *Sequence* in the model will help exclude any confounding effects of (or interaction with) these aspects, especially taking into account that the obtained data will be well-balanced due to the (2x2) study design.

6 Ethical considerations and informed consent

The study shall be conducted in accordance with the ethical principles originating from the *Declaration of Helsinki*²³ and in accordance with *ICH-Good Clinical Practice* (GCP) and applicable regulatory requirements. The study is registered at the local ethics committee with the number 30-468 ex 17/18.

Before randomisation, patients will be comprehensively informed about spermidine and its effects as a compound and the procedures within the trial, but they will be blinded to the treatment sequence (spermidine vs. placebo). Participants will be given the informed consent form and given enough time to consider voluntary participation.

7 Data collection and quality assurance, Data management, Monitoring

A unique ID number will be attributed to every enrolled patient. Patients' names will be protected and accessible only to the personnel/the applicant involved in the study. Blood/serum samples will be stored in an anonymous fashion and biologically destroyed 5 years after completion of the study.

On-site monitoring will be conducted by the KKS (Koordinierungszentrum für Klinische Studien), MedUniGraz. Accuracy and completeness of the CRF entries, source documents, and other study-related documents will be checked. After each monitoring visit, a report of any significant findings/facts, deviations, and deficiencies will be communicated to the investigator.

Conflict of interest:

[name] and [name] declare a potential financial conflict of interest (equity in TLL). They will not analyze any clinical data and will be blinded throughout the lab analysis after the trial.

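### Section 5 analyses change from an unnamed baseline, so the 80% power in Section 2.6 is not tied to the primary analysis; week-0 and week-12 values would serve better as covariates

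*Combined protocol and SAP*

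**What the plan says.** **Analysis.** Section 5 says that the effect of each treatment "will be expressed as a change score from baseline (Δ"). The treatments are then compared in a linear mixed model with subject as a random factor and treatment, period and sequence as fixed factors. No baseline covariate is listed, and the visit that supplies the baseline is not named.

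**Sample size.** Section 2.6 says "we expect a reduction of systolic blood pressure of at least 5 mmHg" and "we calculated that a total of 38 patients would be sufficient to detect that effect at a power of 80"%, with two-sided alpha 5%, "blood pressure variance (SD) of 13 mmHg and within-subject correlation coefficient (r) of 0.65". It does not say whether these inputs describe single readings or changes, or which two visits r connects. The same section motivates the effect with change data: an earlier trial "revealed a drop in systolic blood pressure of 10 mmHg (4.5 mmHg more than in the placebo group").

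**Measurements.** Table 1 in Section 2.2 schedules 24h-BPM at weeks 0, 8, 12 and 20. Section 3.1 agrees: "During each of the four visits patients will be supplied with an ambulatory blood pressure measurement (ABPM) device". A pre-trial value and a post-washout value are therefore both available.

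**Use of the word baseline.** Section 2.1 explains it once, for spermidine: patients "could already have different spermidine levels at baseline (i.e. before starting the trial"). Section 2.1 also lists baseline blood pressure among the patient characteristics that the crossover controls. Section 2.6 uses the term for blood pressure at entry, and Section 4 for the patients' hypertensive starting state. Nowhere is week 12 called a baseline.

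**The concern.** In a 2x2 crossover with a reading at the start and end of each period, change from baseline can mean two things. Subtracting the week-0 value from both end-of-period values removes the same number twice, so it drops out of the within-patient comparison. Subtracting week 0 from week 8 and week 12 from week 20 brings two more noisy readings into the comparison, and these need not cancel.

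Section 2.6 uses one SD and one correlation, and its result fits a comparison of two values per patient. If the primary analysis turned out to be a contrast of four values, the stated power would not describe it. In a small completers-only trial, a true 5 mmHg effect could then be missed more often than planned. The unnamed visit also leaves two primary estimates of different precision open after the data are in.

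**Working it through.** **Inputs from Section 2.6:** difference 5 mmHg, SD 13 mmHg, r 0.65, two-sided alpha 5%, power 80%, 38 completers, 46 enrolled, 15% drop-out. All other correlations below, and the carryover fraction used under the fix, are assumptions, because the documents give a single r.

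**1. Reproduce the 38.** For the difference of two values per patient:

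- SD of difference = 13 × √(2 × (1 − 0.65)) = 10.88 mmHg.
- n = (1.96 + 0.84)² × 2 × 13² × 0.35 / 5² = 7.849 × 118.3 / 25 = 37.1, rounded up to 38.
- Noncentral t with 36 df: noncentrality 5 × √38 / 10.88 = 2.83, power 78.7%.
- With 39 completers (46 × 0.85 = 39.1): 79.8%.

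The plan's figure reproduces.

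**2. Week 0 as the baseline for both periods.** (wk8 − wk0) − (wk20 − wk0) = wk8 − wk20. The baseline cancels, the SD stays 10.88 and power stays 78.7%.

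**3. SD 13 and r 0.65 already describe change scores.** The calculation in step 1 applies as it stands: 78.7%. With period baselines this requires the two period changes to correlate at 0.65. That correlation is 0 whenever all cross-period correlations of the single readings are equal.

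**4. Period baselines subtracted, inputs describing single values.** The contrast is (wk8 − wk0) − (wk20 − wk12). With SD 13 at every visit its variance is

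13² × [4 − 2r(0,8) − 2r(12,20) − 2r(8,20) − 2r(0,12) + 2r(8,12) + 2r(0,20)].

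If all four cross-period correlations are equal they cancel, leaving 4 × 13² × (1 − r_w), where r_w is the within-period correlation. Section 2.6 corresponds to 2 × 13² × (1 − 0.65). The two are equal at r_w = (1 + 0.65) / 2 = 0.825.

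**5. Power at 38 completers,** cross-period r 0.65:

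| Within-period r (assumed) | Contrast SD, period changes | Power, period changes | Power, end values | Power, end values with baseline covariates |
|---|---|---|---|---|
| 0.65 | 15.38 | 49.6% | 78.7% | 77.5% |
| 0.75 | 13.00 | 63.6% | 78.7% | 80.9% |
| 0.80 | 11.63 | 73.2% | 78.7% | 85.2% |
| 0.825 | 10.88 | 78.7% | 78.7% | 88.0% |
| 0.85 | 10.07 | 84.6% | 78.7% | 91.1% |

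For the last column the slope on the within-patient baseline difference is (r_w − 0.65) / 0.35, and the contrast SD is 10.88 × √(1 − slope²). At r_w 0.80 the slope is 0.43 and the SD 9.83. The last column uses 35 df and averages over chance baseline imbalance. Simulation of the crossover agrees with the table to within about half a percentage point.

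**6. Other correlation structures.**

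- Correlation decaying with time, 0.65 at 12 weeks: 59.2% (period changes), 78.7% (end values), 79.3% (covariates).
- Decaying, 0.65 at 8 weeks: 44.7%, 65.7%, 65.6%.
- r_w 0.80, end-to-end and baseline-to-baseline r 0.65, but baseline to the other period's end 0.60: variance 13² × [4 − 4 × 0.80 − 4 × 0.65 + 4 × 0.60] = 13² × 0.60, SD 10.07, power for period changes 84.6%.

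The within-period correlation alone therefore does not fix the power.

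**7. Type I error.** Simulated with no effect at r_w 0.65 and 0.80, all three analyses reject in 4.8% to 5.1% of trials.

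**The case against.** The strongest reply is that the harmless reading is the likelier one. The protocol uses baseline for blood pressure in the sense of the entry value (Sections 2.1, 2.6 and 4), Section 5 uses the singular, and week 12 is only a scheduled visit. Under that reading the baseline cancels and the plan's power stands. This carries weight, but none of those sentences defines the change score. Section 5 attaches a change from baseline to each treatment's effect, and a full set of measurements is taken after washout, which is where a period baseline would come from. The question stays open.

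A second reply is that the lower power figures rest on several conditions at once: period baselines, SD 13 for single values at every visit, 0.65 as the common cross-period correlation, and an assumed within-period correlation. That is correct. A reader might infer from the table that the trial has only 50% to 73% power, or that the 38 was miscalculated. The documents support neither inference. The 38 reproduces, and other correlation structures give power below and above that range.

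A third reply is that naming the baseline visit would be enough and that the covariate model is a choice about efficiency. Naming a common week-0 baseline would indeed restore about 79%. The covariate model is still the better use of readings the trial already takes, as long as its small cost and its mild dependence on washout are accepted.

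**Conclusion.** The point holds as a gap between two sections. Section 5 specifies an unadjusted change score from an unnamed baseline, and Section 2.6 does not say what its SD and correlation measure. About 79% power applies to end-of-period values, to a common week-0 baseline, or if the inputs already describe change scores. If period baselines are subtracted and the inputs describe single values, power could be well below or somewhat above the target, depending on correlations the plan does not state. The 50% to 85% in the table illustrates this for equal cross-period correlations of 0.65 and does not bound it.

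The validity of the test is not in question. The point is worth correcting because it concerns the primary analysis of a small trial and the correction is cheap.

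**What to change.** In Section 5, make end-of-period 24h SBP (weeks 8 and 20) the response in the same mixed model. Enter the week-0 and week-12 values as covariates (patient-mean baseline and within-patient deviation from it) instead of subtracting them. In Section 2.6, say that SD 13 and r 0.65 refer to single values at weeks 8 and 20, if that is what was meant.

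**Cost.** A sentence or two in each section, with no new data or patients.

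- If baselines carry no within-patient information, the covariates lose about one percentage point (77.5% against 78.7%). At within-period r 0.80 they gain (85.2%). They have more power than subtracting period baselines at every correlation in the table and under both decay patterns.
- They do not remove dependence on the true correlations: 65.6% if r 0.65 holds at 8 weeks and decays.
- They rely somewhat on the plan's own assumption, "Although we expect no carryover effects due to the washout period", but less than subtraction does. If 20% of a 5 mmHg effect (assumed) remained at week 12 only, 1 mmHg would shift one of the two sequences. Subtraction would then estimate 5 + 0.5 = 5.5 mmHg. The covariate model would give 5 + 0.5 × slope, that is 5.0 and 5.2 at within-period r 0.65 and 0.80. End values alone, or a common week-0 baseline, would stay at 5.0.

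**If change scores are kept,** either name week 0 as the common baseline for both periods, which keeps about 79%, or name weeks 0 and 12 as the period baselines, state in Section 2.6 what SD 13 and r 0.65 describe, and restate the power for that contrast.

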2.5 Data management / documentation

Data will be collected on paper-based CRFs. CRFs will remain the property of the study center (Medical University of Graz). Data analysis will be performed using SPSS on the institutional computers of the investigators.

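### The plan does not say which baseline period 2 uses; if it is week 12, the random subject effect makes the primary test slightly anticonservative, which a within-patient error term would prevent

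*Combined protocol and SAP*

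**What the plan says.** Section 5 (Statistical considerations and data analysis) says that the effect of each treatment "will be expressed as a change score from baseline (Δ", closing the bracket after the symbol. It then specifies a linear mixed model in which subjects "will be included as a random factor, whereas Treatment (spermidine vs. placebo", period and sequence are fixed. No other covariance structure, estimation method, degrees-of-freedom rule or procedure for a zero variance estimate is given. Section 2.5 adds only that "Data analysis will be performed using SPSS on the institutional computers of the investigators". Section 5 also drops patients who do not complete all four visits, so every analysed patient has two changes.

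The baseline for period 2 is not defined. Two places bear on it and point in different directions:

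- Section 3.1 says "During each of the four visits patients will be supplied with an ambulatory blood pressure measurement (ABPM) device", and Table 1 schedules 24h-BPM at weeks 0, 8, 12 and 20. A start-of-period value at week 12 is therefore available.
- Section 2.1, in a remark about diet, speaks of "different spermidine levels at baseline (i.e. before starting the trial", which is week 0.

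Section 2.6 gives the only correlation in the documents, a "within-subject correlation coefficient (r) of 0.65", with an SD of 13 mmHg.

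**The concern.** In a 2x2 crossover the treatment contrast is within-patient, so its valid error term is the within-patient mean square. A random subject effect gives the same answer as long as the estimated subject variance is positive. That is usual for raw blood pressures, which correlate strongly within a patient. Two changes, each from its own baseline, need not correlate at all. Once the subject variance reaches zero, REML pools the between-patient and within-patient mean squares. It does so only when the between-patient one is smaller, so any departure from the valid error term is downward. The standard error of the primary systolic comparison would then be too small on average and its p-value slightly too favourable.

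**Working it through.** **Inputs.** SD 13 mmHg, r = 0.65, effect 5 mmHg, two-sided 5%, power 80%, 38 evaluable patients (Section 2.6); visits at weeks 0, 8, 12 and 20 (Table 1); completers only (Section 5). The decay of correlation with time in step 3 is an assumption.

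**1. The plan's sample size.** SD of a within-patient difference = 13 × √(2 × (1 − 0.65)) = 10.88 mmHg. n = ((1.960 + 0.842) × 10.88 / 5)² = 37.1, so 38. The plan's figure is reproduced.

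**2. Correlation of the two changes, all visits correlated at r = 0.65** (in units of the visit variance).

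- Own baselines: Cov(Y8 − Y0, Y20 − Y12) = r − r − r + r = 0, so the correlation is 0.
- Common week-0 baseline: Cov(Y8 − Y0, Y20 − Y0) = r − r − r + 1 = 0.35. Each change has variance 2 × 0.35 = 0.70, so the correlation is +0.5.

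**3. Own baselines, correlation decaying with time (assumption).** The covariance is ρ(12) − ρ(4) − ρ(20) + ρ(12). With exponential decay and ρ(12) = 0.65, ρ(4) = 0.866, ρ(8) = 0.750 and ρ(20) = 0.488. The covariance is 1.30 − 0.866 − 0.488 = −0.054, each change has variance 2 × (1 − 0.750) = 0.50, and the correlation is about −0.11. It is negative because weeks 8 and 12 are the closest pair of visits. Other decay patterns that keep 0.65 at 12 weeks give −0.08 to −0.12. Placing 0.65 at 8 weeks instead gives −0.14.

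**4. The error term.** With 38 completers the within-patient (MSW) and between-patient (MSB) mean squares each have 36 df. For changes with variance τ² and correlation c, their expectations are τ²(1 − c) and τ²(1 + c). REML uses MSW if MSB ≥ MSW, and (MSB + MSW)/2 with zero subject variance otherwise. This closed form agreed with direct REML fits (standard errors within 0.2%).

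**5. Size at correlation 0.** The expected shortfall in error variance is half the mean of the positive part of MSW − MSB. That difference has SD τ² × √(2 × 2/36) = 0.333τ². For a normal variable centred at zero the mean positive part is 0.399 × 0.333 = 0.133, and half is 0.067. The error variance is therefore about 7% low, and the root-mean-square SE is √0.933 = 0.966 of its true value. In mmHg, τ² = 2 × 169 × 0.35 = 118.3, the true SE is √(2 × 118.3/38) = 2.50, and the model reports about 2.41.

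**6. Simulation of the two mean squares, 38 completers, no treatment effect.** The ranges for type I error cover 36 versus 72 df when the subject variance is zero, which the plan does not settle. Repeat runs agreed to about 0.1 percentage point.

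| Correlation of changes | Basis | Subject variance zero | Error variance | Type I error |
|---|---|---|---|---|
| +0.5 | week-0 baseline, r = 0.65 | 0.07% | correct | 5.0% |
| +0.2 | assumption | 11% | 1% low | about 5.1% |
| +0.1 | assumption | 27% | 3% low | 5.2–5.3% |
| 0 | own baselines, r = 0.65 | 50% | 7% low | 5.6–5.8% |
| −0.08 to −0.12 | own baselines, assumed decay | 68–77% | 10–13% low | 6.1–6.6% |

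Testing against MSW alone with 36 df gives 5.0% in every row.

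**The case against.** The strongest reply is that the plan's own arithmetic fits the harmless reading. The SD of 10.88 mmHg behind the 38 patients is the SD of week 20 minus week 8, which is what remains when a common week-0 baseline cancels. With own baselines and the same r, the SD is √(2 × 118.3) = 15.4 mmHg and the formula gives 75 patients. This stands as evidence, but it does not settle the matter: Section 2.6 never mentions change scores, and Table 1 repeats the full assessment set at week 12.

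Several stronger statements are tempting but are not supported:

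- *The planned primary p-value is too optimistic.* A reader might infer this outright. It follows only with own baselines and with a correlation of changes near or below zero.
- *A random intercept cannot handle zero correlation.* It can, with a subject variance of zero. Only negative correlation is out of reach. At exactly zero, the trials that hit the bound have the right SE on average (ratio 1.00). The shortfall lies in the other half (ratio 0.93), because MSW is kept only when it is the smaller mean square.
- *The inflation is 6% or more.* That needs decaying correlation, and Section 2.6 gives one value and no decay. A modest positive correlation of +0.2 removes nearly all of the effect.
- *One trial could understate its SE far more.* It can fall well below that trial's own within-patient SE, but the latter is itself a noisy estimate. The average shortfall is about 3% at zero correlation.
- *Every other outcome is affected in the same way.* The documents give no correlation for any other outcome.

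A random subject effect is also a conventional crossover model. Its use is not in itself an error.

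**Conclusion.** The point holds conditionally and is minor. Section 5 leaves the period-2 baseline open. If it is week 12 and all visits correlate at 0.65, the planned model understates the SE by about 3% on average and tests at about 5.6 to 5.8% instead of 5%. If correlation also decays with time so that the changes correlate at −0.08 to −0.12, the level is about 6.1 to 6.6%. If the baseline is week 0 for both periods, or the changes correlate at +0.2 or more, there is practically no inflation. These figures assume REML with a non-negative subject variance, 38 completers and normally distributed data; Section 5 names neither the estimator nor the df method. The reason to act is that the remedy is nearly free and valid under both readings.

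**What to change.** Make two additions to Section 5.

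1. State which visit is the baseline for the period-2 change, week 0 or week 12. If it is week 12, check Section 2.6 against that choice, since its SD of 10.88 mmHg does not describe a difference between two such changes.
2. State that the treatment test uses within-patient variation only, by one of three forms that are equivalent for complete data: (a) subject as a fixed effect, with Treatment and Period (Sequence is absorbed by subject); (b) Treatment, Period and Sequence with an unstructured 2x2 covariance for the two periods (SPSS MIXED, REPEATED statement, type UN) in place of the random subject factor; or (c) a two-sample t test between sequences on each patient's period 1 minus period 2 difference, with n − 2 df.

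The cost is about one line of wording and model syntax. Results are identical to the planned model whenever its subject variance would have been positive. Where it would have been zero, the p-value is slightly less favourable and the interval slightly wider.
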